8.1.3. Vital Sign Measurements

Vital signs include height, weight, temperature, heart rate, respiratory rate, and blood pressure (systolic and diastolic) will be assessed overtime during the study. Descriptive statistics of observed values and change from baseline values will be provided at scheduled visits. The data collected will be summarized by visit. On day 0, where multiple repeat assessments are collected, both the maximum and minimum assessment for each subject will be presented in table summaries. A Corresponding listing will also be provided.

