## 8.2 Prednisone (or Equivalent Corticosteroid)

Prednisone is a glucocorticoid. Glucocorticoids are adrenocortical steroids, both naturally occurring and synthetic, which are readily absorbed from the gastrointestinal tract.

The following adverse reactions (ARs) have been associated with the use of glucocorticoids:

- Thinning of bones (osteoporosis), which may lead to fractures or compressions, especially true of vertebral bodies (backbone).
- Loss of blood supply to bones (aseptic necrosis), which may cause severe bone pain, fractures (especially of the hip and shoulder), and which may require surgical correction.
- High blood pressure (hypertension).
- Increased pressure in the eye (glaucoma).
- Permanent clouding of vision in one or both eyes (cataracts).
- Weight gain with increased appetite and fluid retention.

- Facial fullness.
- Increase in body hair and acne, and tendency to easy bruising and thinning of the skin.
- Increased risk of infections while on high dose continuous steroid therapy.
- Interference with growth.
- Muscle cramps and joint pain.
- Changes in the menstrual cycle.
- Elevations in blood sugar (diabetes).
- Suppression of adrenal glands' ability to make necessary cortisone at times of stress (adrenal insufficiency).
- Irritation of stomach and esophagus with possible ulcer type symptoms and, rarely, bleeding.
- Emotional disturbances.

Dietary guidelines will be provided to subjects while on prednisone or equivalent corticosteroid to help alleviate some of the side effects including blood sugar elevation, associated with the use of glucocorticoids (refer to the Study Reference Manual).

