Visual Acuity Test & Corneal Cludging Exam		X											X					X			X				X	X
VABS-II	X	X											X					X			X	X	X	X	X	X
Neurocognitive Abilities Assessment	X																									
Neurocognitive Abilities Testing (k)		X											X					X			X	X	X	X	X	X
MRI of Liver	X												X					X			X	X	X	X	X	X
MRI of Brain and Cervical Spine (l)		X																X					X			X
ACTH Stimulation (Cosyntropin) Test (m)		X (prior to prednisone)											X													
Liver Biopsy (n)		X											X					X								
Lumbar Puncture (n)		X												X					X							
Immunogenicity Assays (o)		X							X	X			X			X		X			X	X				
Prednisone (or equivalent corticosteroid) Administration (p)		X	X						X																	
SB-318 Infusion			X																							

\* Week 28, 32, 40, 44, and 52 study visits have assessments that do not require evaluation at the clinical site, and therefore may be conducted remotely. Blood and urine samples at these visits may be collected by a qualified home health nurse. For these study visits, GAG testing in urine may be waived for subjects who do not reside in the U.S. Assessments for AEs, concomitant medications and ERT administration log may be conducted remotely over the phone by study staff.

§ Study subjects may participate in the LTFU Study after 12 months of follow-up in this study, in which case an EOS visit may be conducted any time after Week 52 but before the next scheduled study visit. Study participants who wish to enroll in the LTFU Study with less than 12 months of follow-up in this primary study may be considered on a case-by-case basis at the judgement of the Principal Investigator and after consultation with the Sponsor. In these cases, the EOS visit may be conducted at any time on this study.

- Vital signs (height, weight, systolic/diastolic blood pressure, heart rate, respiratory rate, and temperature; for frequency, refer to the Study Reference Manual.
- As permitted by subject's capacity.
- Serum pregnancy test will be performed at Screening and Baseline visits. Urine pregnancy test will be performed on the Day 0 visit if >7 days from Baseline pregnancy test. Urine pregnancy tests will be performed until Week 48 or until 3 consecutive plasma samples are negative for AAV2/6, whichever occurs first.
- Liver panel does not need to be drawn as a separate sample if samples for Clinical Laboratory Tests are obtained at the same visit.

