3.1. Overall Study Design and Plan

This is a Phase 1/2, multicenter, open-label, single-dose, dose-ranging study with sequentially enrolled age cohorts: age ≥ 18 (adult cohorts 1 through 3), age 12 to 17 (pediatric cohorts 4 and 5), and age 5 to 11 (pediatric cohorts 6 and 7). The duration of study participation will be approximately 39 months for each subject, including approximately 3 months for screening followed by 36 months for treatment and study follow-up.

Up to 27 subjects may be enrolled in this study

Subjects who satisfy all inclusion/exclusion criteria will be enrolled into one of the following treatment cohorts:

Cohort	ZFN 1 (SB- 47171) (vg/kg)	ZFN 2 (SB- 47898) (vg/kg)	hIDUA Donor (SB- IDUA) (vg/kg)	Total rAAV (vg/kg)
1	1.00E+12	1.00E+12	8.00E+12	1.00E+13
2	5.00E+12	5.00E+12	4.00E+13	5.00E+13
3	1.20E+13	1.20E+13	9.60E+13	1.20E+14
4	TBD	TBD	TBD	TBD
5	TBD	TBD	TBD	TBD
6	TBD	TBD	TBD	TBD
7	TBD	TBD	TBD	TBD

Subjects who received ERT prior to study enrollment will continue to receive ERT during the study and remain on their current schedule per standard of care unless they undergo protocol-specified ERT withdrawal per protocol. However, ERT will be omitted during the week of the SB-318 infusion to facilitate accurate baseline testing (e.g., of GAG levels in urine, blood, and of IDUA activity in blood) and to allow a week free of ERT after the SB-318 infusion.

Cohort #	Age Range (y)	Total Dose (vg/kg)	# Subjects
1	≥18	1.00E+13	1
2	≥18	5.00E+13	2
3	≥18	1.20E+14	2
4	12-17	TBD	2
5	12-17	TBD	2
6	5-11	TBD	2
7	5-11	TBD	2

For each dose cohort after Cohort 1, two subjects will be dosed at least 4 weeks apart. SMC review will occur after all subjects in each cohort have ≥ 4 weeks of safety data.

The pediatric cohorts will be enrolled only after review of cumulative adult safety data by the SMC. The starting dose for pediatric cohorts 4 through 7 will be decided based on SMC review of study data and must meet pre-defined safety criteria.

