MEAN (SD)	xx.x (xx.xx)	xx.x (xx.xx)	xx.x (xx.xx)	xx.x (xx.xx)	xx.x (xx.xx)	xx.x (xx.xx)
MEDIAN	xx.x	xx.x	xx.x	xx.x	xx.x	xx.x
MIN, MAX	xx, xx	xx, xx	xx, xx	xx, xx	xx, xx	xx, xx
MINIMUM						
n	xx	xx	xx	xx	xx	xx
MEAN (SD)	xx.x (xx.xx)	xx.x (xx.xx)	xx.x (xx.xx)	xx.x (xx.xx)	xx.x (xx.xx)	xx.x (xx.xx)
MEDIAN	xx.x	xx.x	xx.x	xx.x	xx.x	xx.x
MIN, MAX	xx, xx	xx, xx	xx, xx	xx, xx	xx, xx	xx, xx
VISIT X						
n	xx	xx	xx	xx	xx	xx
MEAN (SD)	xx.x (xx.xx)	xx.x (xx.xx)	xx.x (xx.xx)	xx.x (xx.xx)	xx.x (xx.xx)	xx.x (xx.xx)
MEDIAN	xx.x	xx.x	xx.x	xx.x	xx.x	xx.x
MIN, MAX	xx, xx	xx, xx	xx, xx	xx, xx	xx, xx	xx, xx
...						

Note: Baseline is defined as last non-missing measurement prior to dosing. The data collected will be summarized by visit. On day 0, where multiple repeat assessments are collected, both the maximum and minimum assessment for each subject are presented.

[1]Change from baseline: post-baseline value - baseline value. For the change from baseline, only subjects with a value at both baseline and the specific post-baseline timepoint are included.

Source Data: Listing 16.2.8.2

<DIRECTORY PATH>PROGRAM NAME Executed: DDMMYY YYYY hh:mm

Prog Note: Vital sign parameters will be displayed in the same order as the vital sign listing.
The post-baseline visits include Day 0, Day 1, Day 7, Weeks 2, 4, 6, 8, 12, 16, 20, 24, 36, 48, Months 15, 18, 21, 24, 27, 30, 33, 36/EOS, or Early Termination Visit if applicable. Minimum and Maximum assessment rows are included for Day 0 only for all parameters except weight. For weight page, summarize Day 0 in one row, as would be done for any other Visit.

Table 14.3.6
Summary of Electrocardiogram
Safety Set

Visit Parameter	SB-318 1.00E+13 vg/kg (N=xxx)	SB-318 5.00E+13 vg/kg (N=xxx)	Total (N=xxx)
Baseline			
Ventricular Rate (beats/min)			
n	xxx	xxx	xxx
MEAN (SD)	xxx.x (xxx.xx)	xxx.x (xxx.xx)	xxx.x (xxx.xx)
MEDIAN	xxx.x	xxx.x	xxx.x
MIN, MAX	xxx, xxx	xxx, xxx	xxx, xxx
P-R Interval (msec)			
n	xxx	xxx	xxx
MEAN (SD)	xxx.x (xxx.xx)	xxx.x (xxx.xx)	xxx.x (xxx.xx)
MEDIAN	xxx.x	xxx.x	xxx.x
MIN, MAX	xxx, xxx	xxx, xxx	xxx, xxx
QRS Duration (msec)			
n	xxx	xxx	xxx
MEAN (SD)	xxx.x (xxx.xx)	xxx.x (xxx.xx)	xxx.x (xxx.xx)
MEDIAN	xxx.x	xxx.x	xxx.x
MIN, MAX	xxx, xxx	xxx, xxx	xxx, xxx
Q-T Interval (msec)			
n	xxx	xxx	xxx
MEAN (SD)	xxx.x (xxx.xx)	xxx.x (xxx.xx)	xxx.x (xxx.xx)
MEDIAN	xxx.x	xxx.x	xxx.x
MIN, MAX	xxx, xxx	xxx, xxx	xxx, xxx

Source Data: Listing 16.2.8.4

<DIRECTORY PATH>PROGRAM NAME Executed: DDMMYYYY hh:mm

Table 14.3.6

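### If children enrol, the raw height and weight summaries in SAP 8.1.3 cannot show slowed growth; add age- and sex-standardised values for subjects under 18

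*SAP*

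**What the plan says.** SAP 8.1.3 lists height, weight, temperature, heart rate, respiratory rate and blood pressure as vital signs and gives one rule for all of them: "Descriptive statistics of observed values and change from baseline values will be provided at scheduled visits". The Table 14.3.5 shell defines change as the later value minus the baseline value. Its columns are 1.00E+13 vg/kg, 5.00E+13 vg/kg and Total. Neither the SAP text nor the shells contain a z-score, percentile, growth velocity or abnormality category for any vital sign.

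The Protocol's Appendix 1 footnote confirms what is measured: "Vital signs (height, weight, systolic/diastolic blood pressure, heart rate, respiratory rate, and temperature".

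SAP 3.1 plans cohorts 4 and 5 at ages 12 to 17 and cohorts 6 and 7 at ages 5 to 11, with "approximately 3 months for screening followed by 36 months for treatment and study follow-up". All subjects receive prophylactic prednisone or an equivalent, tapered over about 20 weeks (Protocol 3.5 and Appendix 3). Appendix 3 also allows it to be adjusted or restarted. Among the reactions associated with glucocorticoids, Protocol 8.2 lists "Interference with growth" and "Weight gain with increased appetite and fluid retention", as well as hypertension.

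**The concern.** A child's height and weight rise with age whether or not growth is impaired. A raw difference from baseline therefore carries the expected growth as well as any departure from it, and the expected part depends on age and sex. For height, the harm the protocol names is a shortfall against expectation, and the planned table holds no expectation to compare with. For weight, steroid gain and normal growth push in the same direction and the table cannot separate them.

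The layout adds to this. SAP section 4 asks for summaries by treatment cohort and overall, section 8 asks for results by dose level, and the shells use dose columns plus Total. Protocol 11.3 lets children receive only a dose already given to 2 adults. Total therefore pools growing and non-growing subjects, and so does any dose column the two groups share.

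At stake is whether the safety tables can display a child-specific risk of the study's own steroid regimen, from measurements the protocol already collects.

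**Working it through.** **Enrolment (context only).** 1 + 6 × 2 = 13 planned. Adding about 2 in each of 7 cohorts gives 13 + 14 = 27, the stated maximum. Of the 13 planned, 1 + 2 + 2 = 5 are adults and 4 × 2 = 8 are children.

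The documents give no growth rates, steroid effects or reference SDs. All such figures below are assumptions, with linear growth and no catch-up. The steroid window is 20/52 year.

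**Height, assumed 4 to 7 cm/year.**
- Expected gain at Week 24: 4 × 24/52 = 1.8 cm to 7 × 24/52 = 3.2 cm. At Month 36: 12 to 21 cm.
- Deficit from complete arrest for 20 weeks: 4 × 20/52 = 1.5 cm to 7 × 20/52 = 2.7 cm.
- Raw change under that arrest: zero at Week 20, +0.3 to +0.5 cm at Week 24, +10.5 to +18.3 cm at Month 36. It is never negative.
- With half suppression, raw change is already positive at Week 20 (0.8 to 1.3 cm).
- Deficit as a share of the expected 36-month gain: (20/52)/3 = 12.8%, or 6.4% with half suppression.
- A child growing at 5.5 cm/year with complete arrest gains 16.5 − 2.1 = 14.4 cm, well inside the normal 12 to 21 cm.

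**The same deficit on a standardised scale.** With an assumed height-for-age SD of 5 to 7 cm, complete arrest is a fall of 1.54/7 = 0.22 to 2.69/5 = 0.54 SD from the child's own baseline. Half suppression is 0.11 to 0.27 SD. The sign is then negative.

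**Weight, assumed 2 to 5 kg/year growth and 1 to 5 kg steroid excess.**
- Normal gain: 0.8 to 1.9 kg by Week 20, 6 to 15 kg by Month 36.
- Steroid share of raw change at Week 20: 1/(1.92 + 1) = 34% to 5/(0.77 + 5) = 87%.
- At Month 36: 1/16 = 6% to 5/11 = 45%.
- The steroid part is mixed with growth early and diluted later.

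**Systolic pressure, assumed 0.5 to 3 mmHg/year with growth and a 5 to 15 mmHg steroid rise.**
- Steroid share at Week 20: 5/(1.15 + 5) = 81% to 15/(0.19 + 15) = 99%.
- At Month 36, if the rise persisted: 5/14 = 36% to 15/16.5 = 91%.
- Growth hides little during the planned course.

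**Pooling, adults taken as zero growth.**
- A dose column with 2 adults and 2 children has a mean 36-month height change of 2 × 12/4 = 6 cm to 2 × 21/4 = 10.5 cm.
- The Total column at planned enrolment gives 8 × 12/13 = 7.4 cm to 8 × 21/13 = 12.9 cm.
- Neither figure describes the children or the adults.

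**The case against.** The strongest reply is that the summary tables are not the only route. Protocol 10.1.1 makes any worsening sign or examination finding an adverse event, and these are tabulated by term, severity and relationship. Listing 16.2.8.2 shows dated vital signs by subject with age and sex. Cohorts start at 2 children, so a reader could follow each one. This stands in part. Calling slowed growth a worsening still needs an age reference, because height itself goes up, and the vital-signs listing has no reference range or flag of the kind the laboratory listings carry.

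A reader might infer from the programming note to Listing 16.2.8.2 that heights after baseline are dropped. The note does not say so. It offers baseline-only height as an example of showing what was collected at each visit.

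A reader might also infer that steroid hypertension is masked in the same way as growth. The arithmetic does not support that within the roughly 20-week course.

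The study is descriptive, growth is not an endpoint, and raw values are a legitimate display. The shells have no pediatric column, pediatric doses are still to be determined, and the documents do not say whether any child was dosed. That makes the point conditional.

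Finally, standardising does not isolate a drug effect. Protocol 1.1 describes halted growth in the severe form and skeletal deformity. Comparing a child with their own baseline removes a difference in level, but not a disease-driven decline.

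**Conclusion.** The point holds as a cheap improvement, conditional on enrolment of cohorts 4 to 7. For height, the planned tables cannot show the growth interference named in Protocol 8.2: even complete arrest for 20 weeks leaves a positive change from Week 24 onward. For weight, the tables confound growth with steroid gain. For blood pressure the gap is only the lack of an age, sex and height reference, and it is minor.

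Two stronger conclusions are not supported. The documents do not show that the harm would go wholly unreported, since adverse event tables and listings exist. Nor would a fall in z-score establish a prednisone effect, since there is no control group and few children per cohort. The sizes rest on the assumed growth rates, suppression and SD. What does not depend on them is that a raw change contains no expected growth to compare against.

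**What to change.** In SAP 8.1.3 and Table 14.3.5, for subjects under 18 at infusion:
- add height-for-age and weight-for-age (or BMI-for-age) z-scores by sex, with the reference population named in the SAP;
- show each child's value and change from own baseline at every visit;
- present these subjects separately from adults, whatever the dose column, and keep the raw summaries as well;
- state in Listing 16.2.8.2 that height is listed at every visit where it is measured.

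Blood pressure against an age, sex and height reference is optional.

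Add a sentence that the z-scores are descriptive, that a general-population reference fits children with MPS I imperfectly, that the disease can lower z-scores over time, and that change is not to be attributed to prednisone.

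The cost is SAP and shell wording plus a standard derivation from age, sex, height and weight already collected. No assessment, dose or clinical rule changes.

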8.1.4. Physical Examination

Physical examination will be assessed overtime during the study. Results of physical examination at screening is categorized into normal, abnormal and not done. Corresponding listing will be provided.

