#### 6.4 Day 0 (SB-318 Infusion)

Subjects will receive the SB-318 infusion at a hospital or acute care facility, remain there for at least 24 hours after the infusion for observation, and be discharged when all AEs and vital signs are stable.

The following assessments and procedures will be performed:

- Review and record concomitant medications.
- Physical examination.
- Vital signs (for frequency, refer to the Study Reference Manual).
- Assessment of AEs.
- ERT administration log.

- Pregnancy test (females of childbearing potential, only if >7 days from Baseline pregnancy testing).
- Prednisone or equivalent corticosteroid administration.
- Infusion of SB-318 via a peripheral vein catheter.

#### 6.5 Day 1

All subjects will remain in the hospital or acute care facility for at least 24 hours after completion of SB-318 infusion. Subjects will be discharged when all AEs and vital signs are stable.

The following assessments and procedures will be performed:

- Review and record concomitant medications.
- Physical examination.
- Vital signs (continued measurement from Day 0).
- Assessment of AEs.
- Clinical laboratory tests.
- Liver panel.
- Vector genome PCR in plasma (12 hours after end of SB-318 infusion).
- Prednisone or equivalent corticosteroid administration.

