#### 6.7 Weeks 2, 4, 6, and 8 (+/- 2 days)

The following assessments and procedures will be performed unless otherwise stipulated:

- Review and record concomitant medications.
- Physical examination.
- Vital signs.

- Assessment of AEs.
- ERT administration log.
- Pregnancy test (females of childbearing potential only; at Weeks 4 and 8 only).
- Clinical laboratory tests.
- Liver panel (twice weekly; may be conducted remotely).
- GAG testing in urine.
- IDUA / GAG testing in blood.
- Circulating AFP level (at Weeks 4 and 8 only).
- Vector genome PCR in plasma, saliva, urine, stool, and semen (males only; at Weeks 2, 4, and 8 only).
- Immunogenicity assays (at Week 4 only).
- Prednisone or equivalent corticosteroid administration.

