#### **6.8 Weeks 12, 16, 20, 24, 28, 32, 36, 40, 44, 48, and 52 (+/- 1 week)**

The following assessments and procedures will be performed unless otherwise stipulated:

- Review and record concomitant medications.
- Physical examination (at Weeks 12, 16, 20, 24, 36, and 48 only).
- Vital signs (at Weeks 12, 16, 20, 24, 36, and 48 only).
- Assessment of AEs.
- ERT administration log.
- JROM (at Weeks 24 and 48 only).
- Neurologic cranial nerve exam and muscle strength testing of the upper extremities (at Weeks 24 and 48 only).
- 12-lead ECG (at Weeks 24 and 48 only).
- ECHO (at Week 48 only).
- Pregnancy test (females of childbearing potential only; at Weeks 12, 16, 20, 24, 36, and 48 only).
- Clinical laboratory tests (at Weeks 12, 16, 20, 24, 36, and 48 only).
- Liver panel (twice weekly until Week 20; then at Weeks 24, 28, 32, 36, 40, 44, 48, and 52; may be conducted remotely until Week 20 and at Weeks 28, 32, 40, 44, and 52).
- Chimerism assay (at Weeks 12 and 48 only; for post-HSCT subjects only)
- GAG testing in urine.
- IDUA / GAG testing in blood (at Weeks 12, 16, 20, 24, 36, and 48 only).
- Circulating AFP level (at Weeks 12, 24, and 48 only).

- Vector genome PCR in plasma, saliva, urine, stool, and semen (males only) (at Weeks 12, 16, 20, 24, 36, and 48 only).
- PFTs (at Weeks 24 and 48 only).
- 6MWT (at Weeks 24 and 48 only).
- Visual acuity test and corneal clouding exam (at Weeks 24 and 48 only).
- Neurocognitive abilities tests by WASI-II, WPPSI-IV, or BSID-III, and by VABS-II (at Weeks 24 and 48 only).
- MRI of liver (at Weeks 24 and 48 only).
- MRI of brain and cervical spine (at Week 48 only).
- ACTH stimulation (cosyntropin) test (at Week 20 only or at end of prednisone or equivalent corticosteroid taper; see [Appendix 3](#)).
- Liver biopsy (at Weeks 24 and 48 only).
- Lumbar puncture (at Weeks 24 and 48 only).
- Immunogenicity assays (at Weeks 12, 24, 36, and 48 only).
- Prednisone or equivalent corticosteroid administration (through Week 20 only).

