#### **6.9 Months 15, 18, 21, 24, 27, 30, 33, and 36/End of Study (+/-1 month)**

Subjects will be evaluated every 3 months in Years 2 and 3 after SB-318 infusion.

An End of Study (EOS) visit will be conducted at Month 36.

At the EOS visit, subjects will be asked to participate in the LTFU Study. Study subjects may participate in the LTFU Study after 12 months of follow-up in this study, in which case an EOS visit may be conducted anytime after Week 52 but before the next scheduled study visit. Study participants who wish to enroll in the LTFU Study with less than 12 months of follow-up in this primary study may be considered on a case-by-case basis at the judgement of the Principal Investigator and after consultation with the Sponsor. In these cases an EOS visit may be conducted anytime when transition to the LTFU study is imminent. Informed consent will be obtained prior to participating in the LTFU Study.

The following assessments and procedures will be performed unless otherwise stipulated:

- Review and record concomitant medications.
- Physical examination.
- Vital signs.
- Assessment of AEs.
- ERT administration log.
- JROM (at Months 18, 24, 30, and 36/EOS only).
- Neurologic cranial nerve exam and muscle strength testing of the upper extremities (at Months 18, 24, 30, and 36/EOS only).

- 12-lead ECG (at Months 18, 24, 30, and 36/EOS only).
- ECHO (at Months 24 and 36/EOS only).
- Clinical laboratory tests.
- Liver panel.
- Chimerism assay (at Month 36/EOS only; for post-HSCT subjects only)
- GAG testing in urine.
- IDUA / GAG testing in blood.
- Circulating AFP level (at Months 18, 24, 30, and 36/EOS only).
- PFTs (at Months 18, 24, 30, and 36/EOS only).
- 6MWT (at Months 18, 24, 30, and 36/EOS only).
- Visual acuity test and corneal clouding exam (at Months 24 and 36/EOS only).
- Neurocognitive abilities tests by WASI-II, WPPSI-IV, or BSID-III, and by VABS-II (at Months 18, 24, 30, and 36/EOS only).
- MRI of liver (at Months 18, 24, 30 and 36/EOS only).
- MRI of brain and cervical spine (at Months 24 and 36/EOS only).
- Immunogenicity assays (at Months 18 and 24 only).

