### **13.4 Primary Endpoint**

The primary endpoint of this study is the incidence of treatment-emergent AEs (including SAEs). Additional safety evaluations will include:

- Routine hematology, chemistry, and liver function laboratory tests, vital signs, physical exam, ECG, ECHO, and concomitant medications.
- Monitoring of chimerism in post-HSCT subjects.
- Cranial nerve exam and muscle strength testing.
- Serial AFP testing and MRI of liver to evaluate for liver mass.

Safety assessment will be performed on all subjects. All reported AEs will be coded to a standard set of terms using the Medical Dictionary for Regulatory Activities (MedDRA).

Treatment-emergent adverse events will be summarized overall and by treatment cohort. For each subject, the maximum reported severity of each adverse event will be used in the summaries by severity grade. In addition, all serious adverse events and AEs related to study treatment will be summarized.

Laboratory data will be summarized for each time-point at which specimens are collected. Change-from-Baseline values may be calculated for selected laboratory parameters. Shift-tables (Change-from-Baseline relative to the normal range) may be constructed for selected laboratory parameters.

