3.2. Study Endpoints

3.2.1. Primary Endpoints

The primary endpoint of this study is the incidence of treatment-emergent AE's (including SAEs).

Additional safety evaluation will be included:

- Routine hematology, chemistry and liver function laboratory tests, vital signs, physical exam, ECG, ECHO, and concomitant medications.
- Monitoring of chimerism in post-HSCT subjects.
- Cranial nerve exam and muscle strength testing.
- Serial alpha-fetoprotein (AFP) testing and magnetic resonance imaging (MRI) of liver to evaluate for liver mass.

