Prog Note: Sort by Cohort, Subject ID, Date. Actual vital signs may be variable depending on the study & visit. All vitals collected in the study should be in the header, while only those collected at each visit will be displayed in the rows (e.g. height may only be displayed at baseline.). Display only visits where vitals signs are collected and tests done.

Listing 16.2.8.3
Physical Examination at Screening
Enrolled Set

Cohort: SB-318 1.00E+13 vg/kg

Subject ID	Age (yrs) / Sex/ Race	Exam Date (Day)	Assessment	Result	Specify Abnormality
XXXXXX	50/M/W	DDMMYYYY (XX)	Skin Head, Eyes, Ears, Nose, Throat	Abnormal Normal	XXXXXXXXXXXXXXXXXXXX
			...		

Sex: M=Male, F=Female;

Race: W=White, BL=Black or African American, AS=Asian, AI=American Indian or Alaska Native, PI=Native Hawaiian or Other Pacific Islander, O=Other, NS=Not Specified

Day = date of event - date of infusion.

<DIRECTORY PATH>PROGRAM NAME Executed: DDMMYYYY hh:mm

Prog Note: Sort by Cohort, Subject ID, Visit, Exam Date, Assessment. All assessments including Physical Exam, height and weight will be displayed for each subject.

Listing 16.2.8.4
Electrocardiogram
Enrolled Set

Cohort: SB-318 1.00E+13 vg/kg

Subject ID	Age (yrs) / Sex/ Race	ECG Date	Normal Sinus Rhythm	Vent. Rate (bpm)	PR Int (ms)	QRS Dur (ms)	QT Int (ms)	QTc Int (ms)	QRS Axis	Overall Interpretation*
XXXXXX	50/M/W	DDMMYYYY HH:MM (XX)	YES	XXX	XXX	XXX	XXX	XXX	XXX	AB;NCS
XXXXXX	21/F/W	DDMMYYYY HH:MM (XX)	NO	XXX	XXX	XXX	XXX	XXX		AB;CS
XXXXXX	65/F/BL	DDMMYYYY HH:MM (XX)	YES	XXX	XXX	XXX	XXX	XXX	XXX	N

Sex: M=Male, F=Female;

Race: W=White, BL=Black or African American, AS=Asian, AI=American Indian or Alaska Native, PI=Native Hawaiian or Other Pacific Islander, O=Other, NS=Not Specified

Day = date of event - date of infusion.

Vent. Rate=Ventricular Rate (beats/minute), PR Int=PR Interval (milliseconds), QRS Dur=QRS

Duration (milliseconds), QT Int=QT Interval (milliseconds), QTc Int=QT Interval (milliseconds) correction method unspecified

* N=Normal, Ab;NCS=Abnormal;Not Clinically Significant, Ab;CS=Abnormal;Clinically Significant, ND=Not Done

<DIRECTORY PATH>PROGRAM NAME Executed: DDMMYYYY hh:mm

Prog Note: Sort by Cohort, Subject ID, ECG Date.

Listing 16.2.8.5
Echocardiogram
Enrolled Set

Cohort: SB-318 1.00E+13 vg/kg

Subject I	Age (yrs) / Sex / Race	Date of Echocardiogram (Day)	Left Ventricular Ejection Fraction (%)	Results
XXXXXX	50/M/W	DDMMYYYY (XX)	xx	Normal
XXXXXX	65/F/BL	DDMMYYYY (XX)	xx	Abnormal not clinically significant

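### Physical examination is scheduled at 20 post-infusion visits, but SAP 8.1.4 and its only shell, Listing 16.2.8.3, report the Screening examination alone

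*SAP*

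**What the plan says.** Protocol 13.4 gives the safety evaluations that accompany the primary endpoint, starting with "Routine hematology, chemistry, and liver function laboratory tests, vital signs, physical exam, ECG, ECHO, and concomitant medications". SAP 3.2.1 repeats the list. Protocol 9.4 sets a minimum set of body systems for each examination.

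Protocol section 6 schedules the examination at Screening (6.1), Baseline (6.3), Day 0 (6.4), Day 1 (6.5) and Day 7 (6.6). It is listed without restriction in 6.7 for "Weeks 2, 4, 6, and 8" and in 6.9 for "Months 15, 18, 21, 24, 27, 30, 33, and 36/End of Study". Section 6.8 limits it: "Physical examination (at Weeks 12, 16, 20, 24, 36, and 48 only".

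SAP 8.1.4 has three sentences. The first says the examination is repeated during the study. The second is "Results of physical examination at screening is categorized into normal, abnormal and not done". The third promises a listing. That listing is 16.2.8.3, titled "Physical Examination at Screening". Its columns are subject, age/sex/race, examination date with study day, assessment, result and a description of any abnormality. It has no visit column, yet its programming note includes visit among the sort keys. No table shell covers physical examination.

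SAP 4 sets a general default that collected data appear in listings, subject to anything specified elsewhere. SAP 11 declares one change from the protocol's statistical section, which concerns the dose of enzyme replacement therapy.

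**The concern.** A safety evaluation exists to show what happens after dosing. If the specified output stops at Screening, it gives the state of the subjects before SB-318 and nothing after it. The examination cannot then support a statement about post-infusion safety in its own right.

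Listings matter more than usual here. Cohorts start at one or two subjects and every analysis is descriptive, so the subject-level listing carries much of the evidence. A reader of the report could not tell whether a scheduled examination was done, whether it was normal, or whether an abnormality was seen and not reported as an adverse event.

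The gap reaches back before the infusion as well. SAP 4 defines baseline as the last non-missing value before infusion, and Protocol 6.3 schedules a Baseline examination within 21 days of it. Screening may run for about 3 months. A Screening-only listing therefore omits the examination against which worsening from Baseline would be judged under Protocol 10.1.1.

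**Working it through.** The plan gives no figure to reproduce on this point. The check is a count of scheduled examinations, followed by a search for output that shows them.

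**Scheduled post-infusion examinations, subject followed to Month 36**

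| Protocol section | Visits | Count |
|---|---|---|
| 6.5, 6.6 | Days 1 and 7 | 2 |
| 6.7 | Weeks 2, 4, 6, 8 | 4 |
| 6.8 | Weeks 12, 16, 20, 24, 36, 48 | 6 |
| 6.9 | Months 15, 18, 21, 24, 27, 30, 33, 36 | 8 |

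2 + 4 + 6 + 8 = 20.

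Day 0 is left out because 6.4 does not say whether the examination comes before or after the infusion; with it the count is 21. The optional ERT Withdrawal visit (6.11) and its Follow-Up visit (6.13) would add 2 to the 20, giving 22 if they are held separately from regular visits. An Early Termination visit (6.10) also carries an examination. A subject who moves to the long-term follow-up study just after Week 52 would have 2 + 4 + 6 = 12, plus the End of Study examination, which makes 13.

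**Output specified for those examinations**

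- Tables: 0. Vital signs, laboratory tests, ECG, echocardiogram, cranial nerve and muscle strength testing, and liver MRI all have tables that include post-infusion visits. Physical examination has none.
- Listings: one, 16.2.8.3, limited to Screening by its title. Post-infusion visits covered: 0 of 20. Baseline examination covered: no.

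**Does anything else in the SAP bring the later visits in?**

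- The SAP 4 default would, but it yields to a more specific instruction. The text of 8.1.4 and the title of the listing both specify Screening. Two separate places agree, so a stray word in one of them is an unlikely explanation.
- The visit sort key in the programming note points the other way. It has no function in a Screening-only listing. One programmer could follow the title and another the sort key and SAP 4, and they would produce different listings.
- The missing visit column settles nothing by itself, since the ECG and echocardiogram listings lack one too. The wording of 8.1.4 and the title are what restrict the output.
- SAP 11 does not declare that post-infusion examinations will go unreported.

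**The case against.** The strongest objection is the adverse event route. Protocol 10.1.1 counts as an adverse event any examination finding that worsens from Baseline, whether or not it is thought related. SAP 8.1.1 lists all adverse events and tabulates the treatment-emergent ones. A reader might infer from the Screening-only listing that the planned output holds no post-dose finding at all. The documents do not support that: reported worsening appears in Tables 14.3.1.1 to 14.3.3.3 as applicable and in Listing 16.2.7.1, although it is not identified there as an examination finding. What the route cannot show is an examination that was normal, unchanged or not done, or an abnormality that was not reported. It also cannot serve as a check on its own completeness.

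The second objection is that the CRF is not among the documents. Protocol 9.4 says what is examined and refers to manuals for detail; it does not say how results are recorded. The Screening wording would fit a form that takes results by body system at Screening and records later changes as adverse events. This stands. A reader might infer that 20 recorded results per subject are being left out, but a schedule of 20 examinations does not show that 20 categorised results exist.

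Third, a reader might infer that new neurologic or musculoskeletal abnormalities would be invisible. They would not be: cranial nerve and muscle strength results (SAP 8.1.9) and joint range of motion (SAP 8.3.4) are summarised by visit. These are partial substitutes, and dermatologic, respiratory and gastrointestinal examination results have no counterpart of that kind.

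Fourth, Protocol 13.4 prescribes no table for physical examination, so the absence of one breaks no commitment. That also stands. A table of shifts from baseline would add little to a listing with one or two subjects per cohort.

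**Conclusion.** The point holds in a limited form. For a named safety evaluation with 20 scheduled post-infusion examinations, the SAP specifies a Screening-only output: 0 of 20 is listed or tabulated as an examination, and the Baseline examination is also missing. Only worsening reported as an adverse event gets through. Separately, the SAP is inconsistent with itself, because the title of the listing conflicts with its sort order and with the default in SAP 4.

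The count of 20 assumes follow-up to Month 36 and excludes Day 0, early termination and enzyme replacement withdrawal visits. The conclusion about specified output rests on the SAP text and shells alone. Whether results by body system were collected after Screening is unknown, and it decides which correction is right. The plan needs one either way, because 8.1.4 says the examination is repeated during the study and then does not say what becomes of the later results.

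**What to change.** If results after Screening are collected:

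- In SAP 8.1.4, replace *at screening* with *at each scheduled visit*.
- Retitle Listing 16.2.8.3 *Physical Examination*, add a visit column, and show all collected visits, including Baseline and Day 0. The existing sort order then fits.

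If the CRF captures findings after Screening only as adverse events:

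- State in 8.1.4 that post-Screening changes are reported through adverse events, record this in section 11, and remove the visit sort key from the listing.

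No summary table is needed. The first option costs a wording change and one revised listing, with no new data collection provided the results are already on the CRF. The second costs wording only.
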